- 3.22 Co-morbid systemic illnesses or other severe concurrent disease which, in the judgment of the investigator, would make the patient inappropriate for entry into this study or interfere significantly with the proper assessment of safety and toxicity of the prescribed regimens.
- 3.23 Immunocompromised patients (other than that related to the use of corticosteroids) including patients confirmed to be HIV positive or have active viral hepatitis.
- 3.24 Uncontrolled intercurrent illness including, but not limited to, ongoing or active infection, or psychiatric illness/social situations that would limit compliance with study requirements. Patients with any other known concurrent severe and/or uncontrolled medical condition (except carcinoma in-situ), which could compromise participation in the study (e.g. uncontrolled infection, uncontrolled diabetes, chronic active pancreatitis) .
- 3.25 Receiving any other investigational agent which would be considered as a treatment for the primary neoplasm.
- 3.26 Other active malignancy ≤ 1 year prior to registration. EXCEPTIONS: Non-melanotic skin cancer or carcinoma-in-situ of the cervix.
- 3.27 Previous treatment with specific chemotherapy (cytarabine, idarubicin, daunorubicin) or hypomethylating drug (decitabine or azacitidine) for a hematological disorder. EXCEPTIONS: Prior hydroxyurea allowed. Secondary AML is allowed.
- 3.28 Impaired cardiac function including any of the following:
- Inability to monitor the QT interval on ECG
 - Congenital long QT syndrome or a known family history of long QT syndrome.
 - Clinically significant resting brachycardia (< 50 beats per minute)
 - QTc > 450 msec on baseline ECG. NOTE: If the ECG shows a QTc interval greater than 450 msecs at screening triplicates should be performed, one minute apart to confirm the finding (after replacement of any electrolyte imbalance). If 2/3 or 3/3 of the ECGs confirm the QT prolongation (i.e. QTc interval > 450 msecs) the patient must not be included into the trial.
 - Myocardial infarction ≤ 3 months prior to starting study
 - Other clinically significant uncontrolled heart disease (e.g. unstable angina, congestive heart failure or uncontrolled hypertension)
 - History of or presence of clinically significant ventricular, atrial tachyarrhythmias or ejection fraction cutoff
 - Left ventricle ejection fraction $< 45\%$

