4.0 Test Schedule

All routine assessments must be performed within ± 7 days of the day indicated on the Visit Schedule.

Tests and procedures	Pre-Treatment	Active Treatment					
	≤ 7 days prior to registration*	Cycle 1, Day 1	Cycle 1, Day 8	Cycle 1 Day 21	Cycles 2 and above, Day 1	Cycles 2 and above, Day 8 ⁷	Early Discontinuation or End of Treatment
History and exam, weight, vitals, PS	X	X			X	X	X
Height	X						
Adverse event assessment	X	X			X		X
BM testing ²	X				X ²		X
Biomarkers FLT3 Mutation by PCR	X						X
Pregnancy Test	X						
Hematology group(CBC) Hgb, , PLT, WBC with diff. ¹	X	X ¹	X	X	X ¹	X	X
Serum Chemistry (magnesium, potassium, phosphorus, total bilirubin, direct bilirubin ⁵ , alkaline phosphatase, AST, ALT, creatinine)	X	X	X	X	X	X	X
Serum Chemistry (Serum Amylase & Lipase)	X	X			X		X
MUGA/Echo	X						
LDH	X						
Urine analysis (proteinuria, hematuria) ^R	X						
ECG (QTcF results preferred) ^{R 3}	X		X			X ³	X
Patient Medication Diary (Appendix III ⁴)			X		X	X	
Research Correlatives ^{R, 6}	X		X		X ⁶		

* Labs done on the same day of consent but prior to consenting do not need to be repeated.

1. CBC will be done weekly for cycle 1-4. After cycle 4, to be performed Day 1 and Day 8.
2. Bone marrow (BM) sampling will be done upon screening, and day 1 of cycle 3, 5, 9 and then as clinically needed. Recent bone marrow within 21 days (even prior to consenting) will be acceptable and FLT3 PCR could be done on peripheral blood if blasts >10%. Outside FLT3

testing at bone marrow biopsy will be allowed and used if done.

3. ECGs will be performed locally at screening, Day 8 (prior to dosing) of each cycle, and when there's any dose change due to QTc prolongation or re-initiation after a dose interruption. When a dose change occurs due to QTc prolongation or upon re-starting midostaurin, an ECG must be obtained at 7 days afterwards. QTcF results are preferred, however all reporting methods will be accepted.
 4. The diary must begin the day the patient starts taking midostaurin and must be completed per protocol and returned to the treating institution OR compliance must be documented in the medical record by any member of the care team. Patients will be asked to return all unused medication at each visit.
 5. Get direct bilirubin if total bilirubin > upper normal limit.
 6. Correlatives for blood and bone marrow. See section 14.

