7.0 Protocol Treatment

7.1 Treatment Schedule

- 7.11 Patients eligible for the study based on screening tests will be enrolled on the study.
- Patients will proceed to next cycle every 28 days (or later) based on investigator opinion when reviewing each case based on hematological and physical findings.
 - Patients who tolerate combination therapy well and fail to achieve CR/CRi/PR/morphologic leukemia-free state by end of cycle 2, could get midostaurin on days 1-28 of each subsequent cycle, rather than just days 8-21, as per treating MD decision.
 - Patients who achieve a CR/CRi/PR/morphologic leukemia-free state by end of cycle 8 will continue on current regimen.
 - Patients who fail to achieve a CR/CRi/PR/ morphologic leukemia-free state in bone marrow blasts by end of cycle 8 will go to event monitoring.
 - Patients will get a repeat bone marrow biopsy on day one of cycles 3, 5, 9 and then as clinically indicated (see Test Schedule, section 4.0). Patients who achieve CR/CRi will not need repeat bone marrow assessment unless deemed necessary by investigator.
 - Hydroxyurea and/or leukocytapheresis use is allowed to control rising blasts as deemed necessary by treating investigator at any

time.

Cycle length = 28 days (+/- 7 days)

Agent	Dose	Route	Day	Comments
Decitabine ¹	20 mg/m ²	IV	1-5	Could be given days 2-5 by local MD (outside Mayo Clinic).
Midostaurin ²	50 mg twice/day	Oral	8-21	Midostaurin could be given continuously (day 1-28) starting cycle 3 based on MD decision (see 7.11).

1. May be held as per treating physician judgment.
2. If decitabine is held, then midostaurin will be held. If decitabine is administered, midostaurin cannot be held, but can be omitted.

7.12 Maximum cycles of midostaurin are 18, after which a discussion with Novartis will be done on a per patient basis whether to keep patient on continued therapy with the combination of decitabine and midostaurin on study (continue active monitoring per section 4.0).

7.13 If midostaurin is discontinued, single agent Decitabine may be given beyond cycle 18 off protocol until relapse or disease progression off protocol. The patient will go to event monitoring per section 18.0

Note: If single agent Decitabine is being given off protocol, the end of active treatment form should be filled out at the end of cycle 18. Reason treatment ended should be reported as treatment completed per protocol criteria.

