Investigations	Currently the effect of midostaurin on QTc interval prolongation is not fully characterized. Therefore, all patients experiencing a post baseline prolonged QTc interval must have potassium and magnesium checked and any electrolytes imbalances corrected. Additionally, the investigator should consider the risk benefit of any concomitant medications that may prolong the QTc interval. For the purpose of this trial, the correction formula according to Fredericia, i.e. QTcF is being referred to - wherever QTc is mentioned.		
	Electrocardiogram QT corrected interval prolonged- ECG > 450msec	Midostaurin ¹	If the ECG shows a QTc interval greater than 450 msec during the trial, triplicates should be performed, one minute apart to confirm the finding (after replacement of any electrolyte imbalance).
	ECG QTc interval > 450 msec and ≤ 470 msec		Check magnesium and potassium levels and correct any abnormalities. If possible, stop any medications that may prolong the QTc interval. Continue midostaurin at the same dose.
	ECG QTc interval > 470 msec and ≤ 500 msec,		Check magnesium and potassium levels and correct any abnormalities. If possible, stop any medications that may prolong the QTc interval. Decrease midostaurin to 25 mg twice daily 1 dose level for the remainder of the cycle Resume midostaurin at the initial dose in the next cycle provided that QTc interval improves to ≤ 470 msec.

→ → Use the NCI Common Terminology Criteria for Adverse Events (CTCAE) version 4.0 unless otherwise specified ← ←			
CTCAE System/Organ/Class (SOC)	ADVERSE EVENT	AGENT	ACTION
	ECG QTc interval > 500 msec	Midostaurin	Check magnesium and potassium levels and correct any abnormalities. Omit midostaurin for the remainder of the cycle, and, if possible, stop any medications that may prolong the QTc interval. If QTc improves to \leq 470 msec just prior to the next cycle, resume midostaurin at the initial dose. If QTc interval is not improved in time to start the next cycle do not administer midostaurin during that cycle.

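### Section 8.2 defines every QTc as QTcF, but the test schedule accepts any correction without conversion, so one ECG can lead to different entry or dose actions

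*Combined protocol and SAP*

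**What the plan says.** Section 8.2 sets a trial-wide definition: "For the purpose of this trial, the correction formula according to Fredericia, i.e. QTcF is being referred to - wherever QTc is mentioned". Its dose rules then run on QTc:

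- above 450 and up to 470 msec: same dose
- above 470 and up to 500 msec: 25 mg twice daily for the rest of the cycle
- above 500 msec: omit for the rest of the cycle, and resume only at 470 msec or below

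If that recovery has not happened, the instruction is "If QTc interval is not improved in time to start the next cycle do not administer midostaurin during that cycle".

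Section 3.28 excludes patients with "QTc > 450 msec on baseline ECG", subject to confirmation on at least two of three repeat tracings. It names no formula.

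Section 4.0 is looser. The ECG row label reads "ECG (QTcF results preferred)", and footnote 3 says "QTcF results are preferred, however all reporting methods will be accepted". That footnote governs the local ECGs at screening, on "Day 8 (prior to dosing) of each cycle", and after QTc-related dose changes or restarts. These are the ECGs that the rules in 3.28 and 8.2 use.

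**The concern.** Both texts are current. Nothing says which prevails, asks for a value on another correction to be converted, provides for central reading, or gives cut-offs specific to a formula. A reader who accepts the printed QTc, as footnote 3 allows, and compares it with 450, 470 or 500 msec has followed Section 4.0 and departed from 8.2.

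What is at stake is entry and dosing safety. Section 8.2 itself says that the drug's effect on QTc is not yet fully known, and Section 1.2 says that the thorough QTc study could not address the long-acting metabolite at steady state. These rules are therefore a main cardiac safeguard.

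The error can go either way. A reading that is too high can exclude an eligible patient, cut a dose or block a restart. A reading that is too low can admit a patient who should be excluded, or reduce a dose that should be omitted. An admission error also affects evaluability: under 16.11 only eligible patients count, and 16.22 allows 2 patients beyond the 24 required. The QT adverse event graded at each evaluation under 10.51 would mix scales as well.

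**Working it through.** The plan gives no figure on this point to reproduce. The check asks whether the same tracing can fall in different action bands.

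**Inputs from the documents:** cut-offs of 450 msec (3.28) and 450, 470 and 500 msec (8.2); midostaurin 50 mg twice daily on days 8-21 (7.1).

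**Assumptions, not in the documents:** heart rate 50 to 100 bpm, with Bazett as the main alternative and Framingham and Hodges as further ones.

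**Formulas**, with RR = 60/HR in seconds: QTcF = QT/RR^(1/3) and Bazett QTcB = QT/RR^(1/2). Hence QTcB/QTcF = (HR/60)^(1/6), which is 0.9701 at 50 bpm, 1 at 60, 1.0260 at 70 and 1.0491 at 80.

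**Same tracing, two readings:**

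| HR (bpm) | QTcF (msec) | Action on QTcF | Bazett (msec) | Action on Bazett |
|---|---|---|---|---|
| 80 | 440 | eligible | 461.6 | excluded if confirmed |
| 80 | 460 | same dose | 482.6 | reduce |
| 80 | 480 | reduce | 503.6 | omit |
| 50 | 460 | excluded if confirmed | 446.2 | eligible |
| 50 | 505 | omit | 489.9 | reduce |

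**QTcF values that end up on the wrong side of a cut-off** (whole msec). Dividing 450, 470 and 500 by the ratio gives the QTcF at which Bazett reaches each cut-off.

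| HR (bpm) | QTcF where Bazett = 450 / 470 / 500 | Affected at 450 | Affected at 470 | Affected at 500 |
|---|---|---|---|---|
| 50 | 463.9 / 484.5 / 515.4 | 451-463 | 471-484 | 501-515 |
| 70 | 438.6 / 458.1 / 487.3 | 439-450 | 459-470 | 488-500 |
| 80 | 428.9 / 448.0 / 476.6 | 429-450 | all of 451-470 | 477-500 |

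**Other corrections.** Framingham is QT + 154(1 - RR), and Hodges is QT + 1.75(HR - 60). For QTcF 440-505 over 50-100 bpm, the largest gaps from QTcF both occur at QTcF 505:

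- Framingham at 100 bpm: QT = 505 x 0.6^(1/3) = 425.9, so Framingham = 425.9 + 154 x 0.4 = 487.5, a gap of 17.5 msec. An omit becomes a reduce.
- Hodges at 50 bpm: QT = 505 x 1.2^(1/3) = 536.6, so Hodges = 536.6 - 17.5 = 519.1, a gap of 14.1 msec.

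The dose bands are only 20 and 30 msec wide.

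**Triplicates.** The Bazett ratio depends only on heart rate, so repeat tracings one minute apart at the same rate and with the same formula carry the same gap.

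**Dose.** On the days 8-21 schedule the scheduled ECG precedes the first dose of the cycle. A change for the rest of the cycle then covers 14 days: 14 x 2 x 50 = 1,400 mg becomes 14 x 2 x 25 = 700 mg, or 0. After an omission, a recovered QTcF of 460 at 80 bpm reads 483, above the resume limit of 470, so a further cycle passes without the drug.

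**The case against.** The strongest reply is that 8.2 already governs. Its definition is universal on its face, while footnote 3 only says which reports are acceptable and sets no threshold. Read together, any printout may be filed but is judged as QTcF. That reading is available, but it works only if someone recalculates QTcF, and no step tells staff to do so.

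Other points narrow the size:

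- **One institution.** Treatment starts and follow-up takes place at one campus (3.18, 6.9a), which limits variation. It does not fix the formula, since footnote 3 itself expects several.
- **Direction.** Above 60 bpm Bazett errs towards caution, and the unsafe direction needs a slower rate. At 55 bpm the ratio is 0.9856 and the 450 cut-off corresponds to a QTcF of 456.6, so the wrongly admitted band is about 7 msec, against about 14 at 50 bpm. Section 3.28 also excludes clinically significant bradycardia below 50 bpm. This stands for Bazett, but the Framingham example shows an unsafe error at 100 bpm.
- **Dose.** The 14-day figure holds only for the days 8-21 schedule with a pre-dose ECG. Later ECGs affect fewer days. Patients without a response by the end of cycle 2 "could get midostaurin on days 1-28 of each subsequent cycle, rather than just days 8-21"; their ECG moves to day 1 (footnote 7), and a full cycle is 28 x 2 x 50 = 2,800 mg. The cycle 1 day 8 ECG precedes any midostaurin, so a high value there does not plainly trigger a cut under a table headed for treatment-related events.
- **Frequency.** It is unknown and may be low.

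These limit how often and how much. They do not remove the conflict.

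**Conclusion.** The concern holds. Section 8.2 fixes the scale as QTcF, Section 4.0 accepts values on any scale for the same ECGs, and no conversion joins the two. Under Bazett the shift is about -3% at 50 bpm, nil at 60 bpm and about +5% at 80 bpm, enough to move a patient across the entry limit or from one dose action to the next. Framingham and Hodges differ from QTcF by up to about 18 and 14 msec over the values checked.

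The conflict in the text needs no assumption. The sizes depend on the assumed formulas and heart rates, and the number of patients affected cannot be estimated from the documents. The consequences are for eligibility, midostaurin exposure and QT toxicity grading. The 24-patient decision rule, its significance level and its power do not change.

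**What to change.** Amend footnote 3 and the ECG row label in Section 4.0 to require QTcF or, where the printout uses another correction, its calculation from the QT and heart rate on the same tracing before 3.28 or 8.2 is applied. Name QTcF in 3.28. Use the same value to grade QT prolongation under 10.51. Record QT and heart rate on the case report form if it does not already capture them; the forms are not in the documents.

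The cost is a few words in the footnote, the row label and 3.28, at most two data fields, and a simple calculation. No extra ECG is needed, and the change enforces the definition that the protocol already chose.

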5.0 Grouping Factors: None

6.0 Registration Procedures

- 6.1 To register a patient, access the Mayo Clinic Cancer Center (MCCC) web page and enter the registration/randomization application. The registration/randomization application is available 24 hours a day, 7 days a week. Back up and/or system support contact information is available on the Web site. If unable to access the Web site, call the MCCC Registration Office at [REDACTED] [REDACTED] between the hours of 8 a.m. and 4:30 p.m. Central Time (Monday through Friday).

The instructions for the registration/randomization application are available on the MCCC web page (<http://ccswww.mayo.edu/training>) and detail the process for completing and confirming patient registration. Prior to initiation of protocol treatment, this process must be completed in its entirety and a MCCC subject ID number must be available as noted in the instructions. It is the responsibility of the individual registering the patient to confirm the process has been successfully completed prior to release of the study agent. Patient registration via the registration/randomization application can be confirmed in any of the following ways:

- Contact the MCCC Registration Office [REDACTED]. If the patient was fully registered, the MCCC Registration Office staff can access the information from the centralized database and confirm the registration.
 - Refer to “Instructions for Remote Registration” in section “Finding/Displaying Information about A Registered Subject.”
- 6.2 Correlative Research
A mandatory correlative research component is part of this study. The patient will be automatically registered onto this component (See Sections 3.19 and 14.0).
- 6.3 Documentation of IRB approval must be on file in the Registration Office before an investigator may register any patients.

In addition to submitting initial IRB approval documents, ongoing IRB approval documentation must be on file (no less than annually) at the Registration Office [REDACTED]. If the necessary documentation is not submitted in advance of attempting patient registration, the registration will not be accepted and the patient may not be enrolled in the protocol until the situation is resolved.

When the study has been permanently closed to patient enrollment, submission of annual IRB approvals to the Registration Office is no longer necessary.

- 6.4 Prior to accepting the registration, registration application will verify the following:
- IRB approval at the registering institution
 - Patient eligibility
 - Existence of a signed consent form

- Existence of a signed authorization for use and disclosure of protected health information
- 6.5 At the time of registration, the following will be recorded:
- Patient has/has not given permission to store and use his/her sample(s) for future research of AML at Mayo.
 - Patient has/has not given permission to store and use his/her sample(s) for future research to learn, prevent, or treat other health problems.
 - Patient has/has not given permission for MCCC to give his/her sample(s) to researchers at other institutions.
- 6.6 Treatment cannot begin prior to registration and must begin ≤ 7 days after registration.
- 6.7 Pretreatment tests/procedures (see Section 4.0) must be completed within the guidelines specified on the test schedule.
- 6.8 All required baseline symptoms (see Section 10.5) must be documented and graded.
- 6.9a Treatment on this protocol must commence at Mayo Clinic Rochester under the supervision of a hematologist.
- 6.9b Study drug is available on site.

7.0 Protocol Treatment

7.1 Treatment Schedule

- 7.11 Patients eligible for the study based on screening tests will be enrolled on the study.
- Patients will proceed to next cycle every 28 days (or later) based on investigator opinion when reviewing each case based on hematological and physical findings.
 - Patients who tolerate combination therapy well and fail to achieve CR/CRi/PR/morphologic leukemia-free state by end of cycle 2, could get midostaurin on days 1-28 of each subsequent cycle, rather than just days 8-21, as per treating MD decision.
 - Patients who achieve a CR/CRi/PR/morphologic leukemia-free state by end of cycle 8 will continue on current regimen.
 - Patients who fail to achieve a CR/CRi/PR/ morphologic leukemia-free state in bone marrow blasts by end of cycle 8 will go to event monitoring.
 - Patients will get a repeat bone marrow biopsy on day one of cycles 3, 5, 9 and then as clinically indicated (see Test Schedule, section 4.0). Patients who achieve CR/CRi will not need repeat bone marrow assessment unless deemed necessary by investigator.
 - Hydroxyurea and/or leukocytapheresis use is allowed to control rising blasts as deemed necessary by treating investigator at any

time.

Cycle length = 28 days (+/- 7 days)

Agent	Dose	Route	Day	Comments
Decitabine ¹	20 mg/m ²	IV	1-5	Could be given days 2-5 by local MD (outside Mayo Clinic).
Midostaurin ²	50 mg twice/day	Oral	8-21	Midostaurin could be given continuously (day 1-28) starting cycle 3 based on MD decision (see 7.11).

1. May be held as per treating physician judgment.
2. If decitabine is held, then midostaurin will be held. If decitabine is administered, midostaurin cannot be held, but can be omitted.

7.12 Maximum cycles of midostaurin are 18, after which a discussion with Novartis will be done on a per patient basis whether to keep patient on continued therapy with the combination of decitabine and midostaurin on study (continue active monitoring per section 4.0).

7.13 If midostaurin is discontinued, single agent Decitabine may be given beyond cycle 18 off protocol until relapse or disease progression off protocol. The patient will go to event monitoring per section 18.0

Note: If single agent Decitabine is being given off protocol, the end of active treatment form should be filled out at the end of cycle 18. Reason treatment ended should be reported as treatment completed per protocol criteria.

7.14 **Stem Cell Transplantation (SCT):** Allogeneic stem cell transplantation for intermediate and high risk patients (based on treating MD assessment) will be allowed at any time if a suitable donor is found and patient performance status allows. Decitabine and Midostaurin will be discontinued and the patient will go to event monitoring per section 18.0

7.15 If either drug is discontinued during treatment, the patient will go to event monitoring per section 18.0

8.0 Dosage Modification Based on Adverse Events

ALERT: *ADR reporting may be required for some adverse events (See Section 10)*

- Omit = The current dose(s) for the specified drug(s) during a cycle is skipped. The patient does not make up the omitted dose(s) at a later time
- Hold/Delay = The current dose(s) of all drugs during a cycle is delayed. The patient does make up the delayed dose(s) when the patient meets the protocol criteria to restart drugs.
- Discontinue = The specified drug(s) are totally stopped.

Note: If either drug is discontinued during treatment, the patient will go to event monitoring per section 18.0

